5.2.4. Estimand

The same population, ie, all participants with moderate to severe HS for at least one year and meet inclusion/exclusion criteria will be used for all estimands defined below. The FAS (Section 2.4.1.1) will be used to analyze the data.

5.2.4.1. Composite Strategy

The Composite Strategy assesses the treatment effects not only based on the variable measurements, but also based on intercurrent event defined in TF criteria. If a participant meets TF criteria, participant will be a non-responder for binary response variables and no improvement will be assigned for continuous variables.

- **Composite Estimand (Continuous)**

Variables: The endpoint is defined as change for baseline score. No improvement (zero change) will be assigned after a subject meets one or more treatment failure criteria.

Intercurrent Events: the intercurrent events are captured through variable definition.

Population level summary: difference in mean changes from baseline between a guselkumab group and placebo group.

- **Composite Estimand (Binary)**

Variables: The endpoint (e.g. HiSCR) is defined as the proportion of participants achieving a response. No responder status will be assigned after a subject meets one or more TF criteria.

Intercurrent Events: the intercurrent events are captured through variable definition.

Population level summary: difference in proportion of responders between a guselkumab group and placebo group.

The composite strategy will be used for analyzing all efficacy endpoints.

5.2.5. Treatment Groups

In the efficacy analyses, full analysis set will be used and the participants will be analyzed according to the randomized treatment groups they were assigned to, regardless of the treatments they actually received. Unless otherwise specified, efficacy analyses during each of study periods below are in general displayed as follows:

- Analysis through Week 16
 - Efficacy analyses for placebo comparison at Week 16 or through Week 16 will be summarized by randomized treatment group at Week 0:
 - **Placebo:** Participants randomized to placebo group at Week 0.
 - **Guselkumab 200 mg SC:** Participants randomized to guselkumab 200 mg SC group at Week 0.
 - **Guselkumab 1200 mg IV:** Participants randomized to guselkumab 1200 mg IV group at Week 0.
 - Efficacy data from Week 16 through Week 48 will be summarized by the following treatment groups:
 - **Placebo → Guselkumab 100 mg SC:** Participants randomized to placebo group at week 0 and re-randomized at Week 16 to receive guselkumab SC 100 mg.
 - ◆ Only placebo participants who were re-randomized to guselkumab 100 mg SC and received guselkumab 100 mg at Week 16 will be included in the summary for the visits after Week 16.
 - **Placebo → Guselkumab 200 mg SC:** Participants randomized to placebo group at week 0 and re-randomized at Week 16 to receive guselkumab SC 200 mg.
 - ◆ Only placebo participants who were re-randomized to guselkumab 200 mg SC and received guselkumab 200 mg at Week 16 will be included in the summary for the visits after Week 16.

- **Guselkumab 200 mg SC:** Participants randomized to guselkumab 200 mg SC group at Week 0.
- **Guselkumab 1200 mg IV:** Participants randomized to guselkumab 1200 mg IV at Week 0.

These presentations allow assessment of efficacy over time between treatment groups.

5.3. Primary Efficacy Endpoint(s)

5.3.1. Definition

The primary efficacy endpoint is the proportion of patients achieve a HiSCR at Week 16. Refer to Section 5.2.2.1 for the definition of a HiSCR responder.

5.3.2. Analysis Methods

The primary endpoint will be compared between the each guselkumab group and the placebo group. The primary endpoint will be analyzed at Week 16 based on the composite estimand (Section 5.2.4.1) and the data from all participants in FAS (Section 2.4.1.1) will be analyzed according to randomized treatment group regardless of the treatment actually received.

Participants who meet treatment failure criteria prior to Week 16 will be considered nonresponders for the primary endpoint at Week 16. In addition, participants who do not return for evaluation at Week 16 will be considered nonresponders at Week 16.

In this primary analysis, the number and proportion of participants who achieve a HiSCR at Week 16 will be summarized for each treatment group. To address the primary objective, a CMH chi-square statistic stratified by baseline weight (≤ 95 kg, >95 kg) and baseline Hurley stage status at an alpha level of 0.05 will be used for each of the following hypotheses:

1. Guselkumab 1200 mg IV versus placebo in HiSCR at Week 16.
2. Guselkumab 200 mg SC versus placebo in HiSCR at Week 16.

The study is considered positive if at least one of the hypotheses is tested as significant.

5.3.3. Data Handling

The data handling rules specified in Section 5.2.3.3 and 5.2.3.3.1 will be applied to the primary analysis. In the case of participants with missing components (abscess, inflammatory nodule, or draining fistula counts) at Week 16, LOCF will be applied for the missing lesion count(s). This partial component missing data imputation rule will be applied to all the following analyses related to the primary endpoint.

Participants who meet treatment failure criteria specified in Section 5.2.3.2 prior to Week 16 will be considered not achieving HiSCR at Week 16. In addition, for participants who do not return for evaluation at Week 16 will be considered as non-responders.

5.3.4. Sensitivity Analysis

Sensitivity Analysis 1

For participants who do not return for evaluation at Week 16, the analysis will be performed using observed data after applying treatment failure rules (as defined in Section 5.2.3.2).

Sensitivity Analysis 2

A second sensitivity analysis will be performed by using multiple imputations (MI) by treatment group based HiSCR responses respectively. The fully conditional specification (FCS) method will be used to impute the missing data after applying treatment failure for the HiSCR response at Week 16.

More specifically, the missing HiSCR response status will be imputed using FCS method with 50 imputed data sets with seed = 1231 to fill in the missing HiSCR responses through Week 16 in each of the 50 copies of datasets. The proportion difference of HiSCR at Week 16 adjusted for baseline weight (≤ 95 kg, >95 kg) and baseline Hurley stage using Mantel-Haenszel weight between the guselkumab groups and the placebo group and its 95% CI combining multiple datasets will be provided. In addition, the p-value for testing the treatment difference will be obtained from SAS PROC MIANALYZE based on these combined Mantel-Haenszel estimates from the multiple imputation datasets.

5.3.5. Subgroup Analysis

For each of the subgroups defined in Section 2.5, the difference between each of the guselkumab treatment group and placebo group in the proportion of participants achieving HiSCR at Week 16 and its 95% continuity adjusted confidence interval (when the number of participants permits) will be calculated. Subgroup analyses will not be stratified by baseline weight (≤ 95 kg, >95 kg) and baseline Hurley stage status.

In addition, the proportion of participants achieving HiSCR at Week 16 by investigator site/region will be summarized.

5.3.6. Per-protocol Analysis

The primary analyses for primary endpoint will also be performed on per-protocol analysis set (Section 2.4.1.2). Similar treatment failure rules and data handling rules specified in Section 5.2.3 will apply.

5.4. Major Secondary Endpoints

There are 3 major secondary endpoints with 6 corresponding major secondary analyses. They will be performed in the order listed in Figure 2.

- The change from baseline in total AN count at Week 16.
- The change from baseline in DLQI at Week 16.

- The change from baseline in HS-related skin pain in the past 24 hours based on HSSD at Week 16.

This section outlines the definition and analyses of these major secondary endpoints. Data from all participants in FAS (Section 2.4.1.1) will be included and analyzed according to the randomized treatment groups.

5.4.1. Definition

Refer to Section 5.2.2 for the definition of the major secondary endpoints

5.4.2. Analysis Methods

5.4.2.1. The Change from Baseline in Total AN Count at Week 16

For the change from baseline in AN count at Week 16, treatment comparisons will be performed using a Mixed-Effect Model Repeated Measures (MMRM) Model. The MMRM model will include baseline weight (≤ 95 kg, >95 kg), baseline Hurley stage status baseline values, visit, treatment group by visit interaction, and baseline value by visit interaction as explanatory factors.

The model will be performed based on all available data from the 3 treatment groups through Week 16. The treatment difference between a guselkumab group and the placebo group will be estimated by the difference in the least squares means (LSmeans). The 95% CIs for the differences in LSmeans and p-values will be calculated.

5.4.2.2. The Change from Baseline in DLQI at Week 16

The change from baseline in DLQI at Week 16 will be analyzed based on a mixed model (Section 5.2.3.3.2). under the assumption of missing at random (MAR). Marginal mean model will account for treatment group, baseline weight (≤ 95 kg, >95 kg), baseline Hurley stage status, baseline DLQI score, and AN count at each visit up to Week 16 through correlations among these variables. Marginal means will be compared between each of the guselkumab groups and placebo.

In addition, treatment differences and their associated 95% confidence intervals will be presented.

5.4.2.3. The Change from Baseline in HS-related Skin Pain in the Past 24 Hours Based on HSSD at Week 16.

The change from baseline in HS-related skin pain in the past 24 hours based on HSSD at Week 16 will be analyzed based on the analysis approach as specified in Section 5.4.2.1.

5.4.3. Data Handling

Unless otherwise specified, data handling rules specified in Sections 5.2.3.3, 5.2.3.3.2, will be applied to the major secondary analyses.

5.5. Other Efficacy Variable(s)

In addition to the primary and major secondary analyses, the analyses for other efficacy endpoints will be performed and nominal p-values will be provided. Other efficacy endpoints include the endpoints related to

- HiSCR
- Lesion Count
- HS-IGA
- Patient-reported Outcomes
 - HSSD
 - DLQI
 - HADS
 - Patient’s Global Impression of Change (PGIC) of Hidradenitis Suppurativa Severity

The other secondary efficacy analyses outlined in the following sections in general will be carried out at key endpoint (Week 16) and over time.

5.5.1. Definition

Refer to Section 5.2.2 for the definitions of the secondary endpoints described in the following sections.

5.5.2. Analysis Methods

Most of the secondary efficacy analyses described in sections below will be based on FAS. For participants randomized to placebo, only participants who crossed over to receive guselkumab at Week 16 will be included in the efficacy summaries for the visits after Week 16. All statistical testing will be performed at the 2-sided 0.05 significance level. Nominal p-values will be presented.

5.5.2.1. At Week 16

For continuous endpoints related to lesion count and HSSD; where longitudinal data were collected prior to the analysis visits; treatment comparisons will be performed using Mixed-Effect Model Repeated Measure (MMRM) model as specified in Section 5.1 and Section 5.2.3.3.2. For the other continuous endpoints (DLQI components and HADS) with no post baseline data is scheduled to be collected prior to the analysis visit, treatment comparisons will be performed using analysis specified in Section 5.4.2.2.

For binary response endpoints treatment comparisons will be performed using a Cochran-Mantel-Haenszel (CMH) test stratified by the baseline weight (≤ 95 kg, >95 kg) and baseline Hurley stage status with missing data imputed with Non-Responder Imputation (NRI) defined in Section 5.1.

5.5.2.2. Over Time Summaries

In general, all endpoints with over time analyses will be descriptively summarized by treatment groups using descriptive statistics, such as mean, median, standard deviation, interquartile range, minimum and maximum for continuous variables, and counts and percentages for categorical variables.

Through Week 16

For selected continuous endpoints (change from baseline in AN count, abscess, inflammatory nodule, and draining fistula), Mixed-Effect Model Repeated Measure (MMRM) model will be used and Least Square means (LS means), LS means differences and their corresponding 95% confidence interval will be provided overtime through Week 16 by visit and treatment group in addition to the descriptive summary statistics based on observed data after treatment failures.

From Week 16 through Week 48

For selected continuous endpoints (change from baseline in AN count, abscess, inflammatory nodule, and draining fistula), Mixed-Effect Model Repeated Measure (MMRM) model will be used, Least Square means (LS means) and the corresponding 95% confidence intervals will be provided over time from Week 16 through Week 48 by visit and treatment group in addition to the descriptive summary statistics based on observed data after treatment failures.

Furthermore, for the over time summaries in proportion of participants achieving HiSCR and HS-IGA score of 0 or 1, the corresponding 95% CIs will also be provided for each treatment group at Week 40.

Additionally, the following overtime analyses will be performed at Week 16 DBL with the data available at the time of Week 16 database lock. These analyses will be performed based on the observed data without applying treatment failure rules.

- The proportion of participants who achieved HiSCR from Week 16 through Week 48.
- The change from baseline in total AN count from Week 16 through Week 48.
- The proportion of participants with HS-IGA score of inactive (0), HS-IGA score of inactive (0) or almost inactive (1), and the proportion of participants achieving HS-IGA score of mild activity or better (≤ 2) from Week 16 through Week 48.
- The change from baseline for the past 24 hours pain from Week 16 through Week 48.

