2.4. Analysis Sets

There will be at least two database locks at Weeks 16 and 48 respectively, but additional locks may be performed.

Week 16 database lock

Week 16 database lock will include all data through Week 16 for all randomized participants. In addition, the available data through Week 48 by the time the last participant completes Week 16 visit will also be included. The additional data will be primarily used to assess the maintenance of clinical response through week 48 in planning for future clinical development in HS; selected efficacy, safety, and PK/PD analyses (Section 5.5, 6.1, and 7.1.1) with the data through Week 48 will be included in Week 16 database lock.

Week 48 database lock

Week 48 DBL would include all data through Week 48 for all randomized participants.

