5.5.3. Data Handling Rule

Unless otherwise specified, data handling rules specified in Section 5.2.3.3 will be applied to these secondary analyses. Over time summaries for continuous endpoints will be based on the observed data after treatment failure rules. For binary endpoints, participants with missing response status after applying treatment failures rules will be considered non-responders for the over time analyses.

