5.5.4. Analysis Related to HiSCR

- The proportion of participants who achieved HiSCR, the proportion of participants who achieved HiSCR by baseline weight (≤ 95 kg, >95 kg), and the proportion of participants who achieved HiSCR by baseline Hurley stage status will be summarized by treatment group over time.

The proportion of participants who achieved HiSCR will also be summarized over time by treatment groups using observed data after applying treatment failure rules and observed data without considering treatment failure rules respectively as sensitivity analyses.

In addition, the HiSCR will be summarized over time from Week 20 through Week 48 with Week 16 as baseline for the placebo participants who are re-randomized to either guselkumab 100 mg q8w or guselkumab 200 mg q4w group.

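### For the Week 16 lock, SAP 5.5.2.2 names post-Week-16 HiSCR and HS-IGA rates only on observed data without treatment-failure rules; these may be optimistic for planning, and a failure-rule version beside them is a cheap improvement

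*SAP*

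**What the plan says.** SAP 2.4 describes the data in the Week 16 lock. Beyond Week 16 itself, "the available data through Week 48 by the time the last participant completes Week 16 visit will also be included". These additional data are "primarily used to assess the maintenance of clinical response through week 48 in planning for future clinical development in HS". On scope, "selected efficacy, safety, and PK/PD analyses (Section 5.5, 6.1, and 7.1.1) with the data through Week 48 will be included"; the selection is not itemised.

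SAP 5.5.2.2 then lists four post-Week-16 analyses for that lock: HiSCR, change in AN count, HS-IGA categories (0; 0 or 1; 2 or less) and change in 24-hour pain. On their handling it says: "These analyses will be performed based on the observed data without applying treatment failure rules".

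The default elsewhere differs:

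- SAP 5.2.3.2 makes a treatment failure persist from its onset, with non-responder status for binary variables.
- SAP 5.5.3 says: "For binary endpoints, participants with missing response status after applying treatment failures rules will be considered non-responders for the over time analyses". It opens with an exception clause: "Unless otherwise specified, data handling rules specified in Section 5.2.3.3 will be applied to these secondary analyses".
- SAP 5.2.4.1 says: "The composite strategy will be used for analyzing all efficacy endpoints". It mentions neither this exception nor the one in SAP 5.5.8.
- SAP 5.5.4, for HiSCR only, describes summaries on "observed data without considering treatment failure rules respectively as sensitivity analyses".

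**The concern.** In SAP 5.5.4 the HiSCR version without failure rules is a sensitivity analysis. For the post-Week-16 read-out at the Week 16 lock, it is the only version named. Two things can raise a response rate computed this way. A participant who has met a failure criterion but still attends can count as a responder. A participant who was due but is absent drops out of the denominator.

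Absence can be related to outcome. Protocol 6.5.1 requires study drug to stop if a lesion intervention is needed after Week 16. Protocol 7.1 continues visits for only about 12 weeks after the last dose. A last dose at Week 24 takes follow-up to about Week 36, so such a participant will usually have no Week 40 assessment. (Protocol 6.3 and 8.2.11.2 provide for longer attendance in particular cases.)

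At stake is how well response appears to be maintained when further development is planned.

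**Working it through.** The plan states no figure on this point, so there is nothing to reproduce. The direction can be settled exactly; the size can only be illustrated.

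**Direction.** Take the participants due at one visit in one group. Let A, B, C be those without treatment failure who are observed responders, observed non-responders and missing. Let D, E, F be the same three categories among treatment failures.

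- Observed, no failure rules: (A + D) / (A + B + D + E)
- Failure and missing both non-response: A / (A + B + C + D + E + F)

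The first numerator is never smaller and the first denominator never larger, so the first rate is never lower. They are equal when no failure responds and nobody due is absent (or when there are no responders at all). Enumerating all counts from 0 to 6 in the six categories (117,600 cases with someone observed) gave no reversal and 2,646 ties.

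**Conditions.**

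1. The same participants are compared in both versions.
2. Partly missing lesion counts are carried forward in both versions. If observed data were read as dropping that rule, HiSCR could reverse slightly, for example 30/59 = 50.8% against 31/60 = 51.7%. SAP 5.3.3 extends the rule to all later analyses related to the primary endpoint, which argues against that reading.
3. For HS-IGA of 2 or less, non-responder status takes precedence over the baseline-value substitution in SAP 5.2.3.2. Otherwise a failure whose baseline score was already 2 or less would count as a responder.

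**Size, all inputs assumed.** Let r be the response rate without failure, m the share of those due who are absent, a the share failed but attending, and q the response rate among that last group.

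- Observed = [(1 − a − m)r + aq] / (1 − m)
- Failure-rule = (1 − a − m)r

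| r | a | m | q | Observed | Failure-rule | Gap (points) |
|---|---|---|---|---|---|---|
| 55% | 0 | 0 | – | 55.0% | 55.0% | 0 |
| 55% | 0 | 5% | – | 55.0% | 52.25% | 2.75 |
| 55% | 0 | 10% | – | 55.0% | 49.5% | 5.5 |
| 55% | 0 | 20% | – | 55.0% | 44.0% | 11.0 |
| 55% | 5% | 0 | 0 to 55% | 52.25–55.0% | 52.25% | 0–2.75 |
| 55% | 5% | 10% | 0 to 55% | 51.9–55.0% | 46.75% | 5.2–8.25 |
| 30% (HS-IGA) | 0 | 5%, 10%, 20% | – | 30.0% | 28.5%, 27.0%, 24.0% | 1.5, 3.0, 6.0 |

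**In counts.** With even enrolment over T weeks, the share due at Week 40 when the last participant reaches Week 16 is 1 − 24/T. Of 60 per guselkumab group that is 24 (T = 40), 32 (T = 52) or 42 (T = 78). If 3 of 32 are absent and 16 respond, the observed version reports 16/29 = 55.2% and the failure-rule version 16/32 = 50.0%. The 95% half-width, 1.96 × √(0.55 × 0.45 / n), is about 17 points at n = 32 and 13 at n = 60.

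**Why no direction is claimed for AN count.** Suppose 10% are attending failures and the others average −5. With failure rules (zero change for failures) the mean is 0.9 × (−5) = −4.5. Without them it is −4.8 if the failures average −3, and −4.3 if they average +2. Participants missing for other reasons stay missing in both versions (SAP 5.2.3.3.2).

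**The case against.** The strongest reply is that this is a disclosed, descriptive analysis, sensibly chosen for a partial data cut. Most of that stands.

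- A reader might infer that SAP 5.5.2.2 breaches the composite strategy. It does not: SAP 5.5.3 allows for exceptions and 5.5.2.2 states one openly. The general sentence in 5.2.4.1 lacks only a cross-reference.
- A reader might infer that no failure-rule version will exist at this lock. The documents do not say so. The four analyses are introduced as additional to summaries that do apply the failure rules. SAP 5.5.4 and 5.5.6 plan over-time HiSCR and HS-IGA summaries under the default handling. SAP Section 2 says the plan serves both locks. But none of these summaries is tied to the Week 16 lock, and SAP 2.4 promises only a selection.
- Applying the missing-is-non-response rule to visits not yet due would be artificial. In the example above it would give 16/60 = 26.7%. The fair comparator counts only participants due by the cut. That denominator is proposed here; the SAP does not define it.
- A reader might infer that Week 16-lock rates must exceed Week 48-lock rates. They need not, because the participants differ.
- A reader might take these observed rates to be the planning figure. SAP 2.4 gives the additional data a planning purpose, but attaches no decision rule to these rates.

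What the reply does not remove is the one-way direction for the two binary endpoints, whenever failures respond or participants who were due are absent.

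**Conclusion.** This is a cheap improvement, not an error in the plan. Under the three conditions above, the HiSCR and HS-IGA proportions named for the Week 16 lock can only equal or exceed those that count failures and missing responses as non-response, so the maintenance rates may be optimistic. The documents give no failure, stopping or enrolment rates, so the amount cannot be estimated and may be zero. The illustrated gaps of 0 to 11 points are assumptions and lie within the sampling error of a single group's rate, but they cannot run the other way. A reader might extend the point to all four listed endpoints; the documents do not support that, since no direction follows for AN count or 24-hour pain. The primary test, the major secondary tests and the Week 48-lock summaries are unaffected.

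**What to change.** In the Week 16-lock block of SAP 5.5.2.2, add a second version of the HiSCR and HS-IGA proportions. It should apply the SAP 5.2.3.2 rules and count missing response as non-response among participants whose scheduled visit date is on or before the data cut. Show it beside the observed-data version, with the number due and the number observed for each visit and group.

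Optional wording:

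- Say whether the rule counting rescued lesions as present applies in the observed version. It sits within SAP 5.2.3.2 and can decide response: with a baseline AN count of 3, HiSCR needs 1 or fewer, and two rescued lesions counted as present rule it out.
- In SAP 5.2.4.1, cross-reference the exceptions in 5.5.2.2 and 5.5.8.

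The cost is SAP wording and one more descriptive table set. The figures may look slightly less favourable, and numbers at late visits will be small.
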